#### **7.1.8. Physical Examination**

A listing will be presented for all physical examination data.

#### **7.1.9. Neurological Examination**

A listing will be presented for all neurological examination data.

#### **7.1.10. Concomitant Medications**

All concomitant medications will be coded using the WHO Drug. The incidence of concomitant medications will be summarized using descriptive statistics by therapeutic class and preferred term. Patients are counted only once in each therapeutic class category, and only once in each preferred term category. Concomitant medications will include all medications taken while the patient takes study drug.

In addition, separate summaries will be presented including only concomitant medications prior to baseline and concomitant medications that started post baseline.

#### **7.1.11. Other Safety Assessments**

Summary statistics for the UPDRS motor score and subscale scores will be presented at baseline of this study and each Part A visit that this is measured. UPDRS motor score and subscale scores values and changes from baseline of this study to each visit will be summarized using descriptive statistics.

Summary statistics for the BARS summary score will be presented at baseline of this study and each Part A visit that this is measured. BARS summary score values and changes from baseline of this study to each visit will be summarized using descriptive statistics.

Summary statistics for the HADS depression and anxiety subscales scores will be presented at baseline of this study and each Part A visit that this is measured. HADS subscale values and changes from baseline of this study to each visit will be summarized using descriptive statistics.

Summary statistics for the C-SSRS baseline version will be presented at screening and for the C-SSRS last visit version will be presented at baseline of this study and each Part A visit that this is measured. Patients with suicidal ideation and behavior items as well as self-injurious behavior without suicidal intent will be summarized at each visit as categorical data using descriptive statistics.

Also for C-SSRS, patients with suicidal ideation and behavior items as well as self-injurious behavior without suicidal intent will be summarized at anytime postbaseline as categorical data using descriptive statistics. Shifts (yes, no) from baseline of this study to anytime postbaseline will be summarized using patient counts for the suicidal ideation and behavior categories as well self-injurious behavior without suicide intent.

Summary statistics for the ESS total score will be presented at baseline of this study and each Part A visit that this is measured. ESS total score values and changes from baseline of this study to each visit will be summarized using descriptive statistics.

Summary statistics for the MoCA® total score will be presented at baseline of this study and each Part A visit that this is measured. MoCA® total score values and changes from baseline of this study to each visit will be summarized using descriptive statistics.

## **7.2. Part B**

### **7.2.1. General**

The randomized withdrawal ITT population will be used for all Part B safety summaries. Summaries will be presented by randomized withdrawal treatment group (SD-809 and placebo) and overall for Part B visits.

### **7.2.2. Study Drug Administration**

Total daily dose (mg) will be summarized as continuous data at each Part B visit using descriptive statistics.

### **7.2.3. Adverse Events**

All AEs in the Part B Randomized Withdrawal Period will be summarized using descriptive statistics by system organ class and preferred term.

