**Part B:**

Part B will consist of a double-blind; randomized withdrawal period; treatment with SD-809; and post-treatment safety follow-up. The Randomized Withdrawal Period will be 1 week (+3 days

maximum) in duration and will consist of 2 visits, the Pre-withdrawal Visit and the Post-withdrawal Visit. After the Randomized Withdrawal Period, the subjects will resume treatment with SD-809 on the prior established dose for an additional 12 weeks until end of treatment (EOT). A follow-up telephone call will occur 4 weeks after EOT.

At the beginning of the Randomized Withdrawal Period, subjects will be randomized in a blinded fashion to either SD-809 (current dose) or placebo in a 1:1 ratio stratified by concomitant DRA usage. Up to 194 subjects (active subjects as of the approval date of Amendment 06) will be randomized (SD-809 or placebo). Subjects will be required to sign a written informed consent.

Subjects will need to be on a stable dose of SD-809 and any concomitant DRA for a minimum of 4 weeks before starting the Randomized Withdrawal Period.

Subjects will be scheduled to return 1 week (+3 days maximum) after the Pre-withdrawal Visit of the Randomized Withdrawal Period for efficacy and safety assessments.

At the end of this period, subjects will continue treatment with SD-809 at the previous dose administered before the Randomized Withdrawal Period (last dose in Part A). Treatment with SD-809 will continue for 12 weeks until the EOT visit.

Video ratings of the AIMS will occur at the Pre-withdrawal Visit, the Post-withdrawal Visit, and the EOT/early termination (ET) visit.

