#### **8.4. Safety Endpoints**

The following safety endpoints will be assessed in Part A:

- Incidence of adverse events, serious adverse events, severe adverse events, drug-related adverse events, adverse events leading to withdrawal during the following periods:
  - Overall
  - During titration
  - During long-term treatment
- Observed values and changes from baseline in clinical laboratory parameters (hematology, chemistry, and urinalysis)
- Observed values and changes from baseline in vital signs
- Observed values in ECG parameters and abnormal findings
- Number of subjects with on-treatment QTcF values >450 ms, >480 ms, >500 ms, or a change from Baseline in QTcF of >30 ms or >60 ms
- Observed values and changes in UPDRS Part III (motor examination), BARS, HADS, C-SSRS, ESS, and MoCA©
- Duration of time to achieve stable dosing of SD-809

The following secondary safety endpoints will be assessed in Part B:

- Incidence of adverse events, serious adverse events, severe adverse events, drug-related adverse events, and adverse events leading to withdrawal
- Observed values and changes from start of randomized withdrawal in clinical laboratory parameters (hematology, chemistry, and urinalysis)
- Observed values and changes from start of randomized withdrawal in vital signs
- Observed values in ECG parameters and abnormal findings
- Number of subjects with on-treatment QTcF values >450 ms, >480 ms, >500 ms, or a change from Baseline in QTcF of >30 ms or >60 ms
- Observed values and changes in UPDRS Part III (motor examination), BARS, HADS, C-SSRS, ESS, and MoCA©

The following secondary safety endpoints will be assessed in Part C:

- Secondary safety endpoints:
  - Incidence of adverse events, serious adverse events, severe adverse events, drug-related adverse events, and adverse events leading to withdrawal from start of Part C
  - Observed values and changes in vital signs from start of Part C
  - Observed values and changes in C-SSRS from start of Part C
  - Observed values in ECG parameters and abnormal findings from start of Part C

- Number of subjects with on-treatment QTcF values >450 ms, >480 ms, >500 ms, or a change from Baseline in QTcF of >30 ms or >60 ms from start of Part C

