## 2.2. Primary and Secondary Measures and Endpoints

### 2.2.1. Safety Measures and Endpoints

The safety measures and endpoints in Part A are as follows:

1. Incidence of AEs, SAEs, severe AEs, drug related AEs, AEs leading to withdrawal, AEs leading to dose reduction, AEs leading to dose suspension during the following periods: overall, during titration, and during long-term treatment
2. Observed values and changes from baseline in clinical laboratory parameters (hematology, chemistry, and urinalysis)
3. Observed values and changes from baseline in vital signs
4. Observed values in electrocardiogram (ECG) parameters and abnormal findings
5. Number of patients with on-treatment QTcF (Fridericia-corrected QT interval) values >450 ms, >480 ms, >500 ms, or a change from baseline in QTcF of >30 ms or >60 ms.
6. Observed values and changes in Unified Parkinson's Disease Rating Scale (UPDRS) Part III (motor examination), Barnes Akathisia Rating Scale (BARS), Hospital Anxiety and Depression Scale (HADS), Columbia-Suicide Severity Rating Scale (C-SSRS), Epworth Sleepiness Scale (ESS), and MoCA® (Montreal Cognitive Assessment)

The safety measures and endpoints in Part B (Randomized Withdrawal Period) are as follows:

1. Incidence of adverse events, serious adverse events, drug-related adverse events, and adverse events leading to withdrawal.
2. Observed values and changes from start of randomized withdrawal in clinical laboratory parameters (hematology, chemistry, and urinalysis)
3. Observed values and changes from start of randomized withdrawal in vital signs
4. Observed values in electrocardiogram (ECG) parameters and abnormal findings
5. Number of patients with on-treatment QTcF (Fridericia-corrected QT interval) values >450 ms, >480 ms, >500 ms, or a change from baseline in QTcF of >30 ms or >60 ms.
6. Observed values and changes in UPDRS Part III (motor examination), BARS, HADS, C-SSRS, ESS, and MoCA®

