**Part A and B Combined:**

Some analyses, such as the analyses of adverse events, will be performed by time period. For these analyses, the following definitions will be used:

- Titration Period - from the first dose of treatment until 7 days after the week 6 visit. If a patient discontinues treatment before 7 days after the week 6 visit, then the Titration Period is until the last dose of treatment.
- Maintenance Period - from 8 days after the week 6 visit until the day of the week 158 visit for patients only in Part A and until the day of the open-label treatment EOT visit for patients in both Parts A and B. If a patient enters the Maintenance Period but discontinues treatment early, the Maintenance Period is until the last dose of treatment.

- Overall Treatment Period - includes the Titration and the Maintenance Periods, if applicable.
- Follow-up Period - from the end of the Overall Treatment Period through the end of the study.

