## **7. SAFETY ANALYSIS**

### **7.1. Part A**

#### **7.1.1. General**

The safety population will be used for all safety summaries. Summaries will be presented by parent study treatment group and overall. Summaries will be presented for Parts A and B combined unless otherwise noted.

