In addition, the exposure-adjusted incidence rate (EAIR) of AEs in the overall treatment period will be presented for the overview of AEs, AEs by SOC and preferred terms, and the SMQ summaries. EAIR is calculated as the number of patients with an AE divided by patient-years of treatment. For calculating patient years, patients with an AE contribute with treatment exposure up to the day of their first AE, patients without an AE contribute their entire treatment duration in Parts A and B combined as described above for the censoring if patients do not experience an event.

The EAIR for all AEs in the overall treatment period and for SMQ categories will be summarized by the time periods of <15 weeks,  $\geq 15$  to <54 weeks,  $\geq 54$  to <106 weeks,  $\geq 106$  to <158 weeks, and  $\geq 158$  weeks using descriptive statistics.

All AEs in the overall treatment period that occurred in  $\geq 4\%$  of patients will be summarized by preferred term using descriptive statistics.

Listings for AEs leading to death, serious AEs, AEs causing discontinuation, AEs leading to dose reduction, and AEs leading to dose suspension will be presented.

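### Part B adverse events are tabulated by randomised arm only for the 7–10 day withdrawal period, so restart at full dose after placebo is not compared with continued treatment

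*SAP*

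**What the plan says.** Protocol 3.1 describes Part B in three stages: "Part B will consist of a double-blind; randomized withdrawal period; treatment with SD-809; and post-treatment safety follow-up". The withdrawal period lasts 7 days, or up to 10. Under Protocol 5.2.3, patients take their pre-withdrawal dose of SD-809 from the day after the Post-withdrawal Visit, for 12 weeks.

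Protocol 8.4 gives the first Part B safety endpoint as "Incidence of adverse events, serious adverse events, severe adverse events, drug-related adverse events, and adverse events leading to withdrawal". The list applies to Part B as a whole.

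SAP 2.2.1 narrows the scope in its lead-in, "The safety measures and endpoints in Part B (Randomized Withdrawal Period) are as follows", and its first item reads "Incidence of adverse events, serious adverse events, drug-related adverse events, and adverse events leading to withdrawal". Severe events are missing.

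SAP 7.2.1 groups Part B safety summaries by randomised withdrawal arm. The adverse event plan in SAP 7.2.3 is one sentence: "All AEs in the Part B Randomized Withdrawal Period will be summarized using descriptive statistics by system organ class and preferred term".

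Open-label events fall under SAP 7.1.1: "Summaries will be presented by parent study treatment group and overall. Summaries will be presented for Parts A and B combined unless otherwise noted". In SAP 4.5 the Maintenance Period runs "until the day of the open-label treatment EOT visit for patients in both Parts A and B". SAP 7.1.3 adds patient listings: "Listings for AEs leading to death, serious AEs, AEs causing discontinuation, AEs leading to dose reduction", and those leading to dose suspension. SAP section 9 records one change from the protocol, on ECG variables by visit, and does not mention this narrowing.

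**The concern.** About half of the Part B patients come off active drug for 7–10 days and then, by default, return in one step to their earlier dose. The other half continue without a gap. Allocation was random, so this is the study's only randomised contrast of full-dose restart with uninterrupted treatment.

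SAP 7.2.4 to 7.2.7 carry laboratory tests, vital signs, ECG shifts and rating scales through to EOT by withdrawal arm. After the Post-withdrawal Visit, however, these are next scheduled at EOT about 12 weeks later, and SAP 4.5 excludes unscheduled open-label visits from the Part B analyses. A reaction to restart that came and went in between would show mainly as an adverse event. That is the one type of safety data whose by-arm summary stops when the withdrawal period ends.

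**Working it through.** **1. The plan's own figures.** No figure is stated for the adverse event analysis. The Part B sample size (SAP 2.3) fixes the arm sizes, so it was checked. With difference 1.4, SD 2.9, two-sided 5% and 90% power:

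n = 2 × (1.960 + 1.282)² × 2.9² / 1.4² ≈ 90.2, so 91 per arm, as stated.

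With 143 randomised, 143/2 = 71.5 per arm, and power is 82.3% (normal) or 81.8% (noncentral t), consistent with the stated approximate 80%. Actual arm sizes are not given; 71–72 follows from 1:1 allocation.

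**2. Share of Part B treatment time covered by the by-arm table.** Withdrawal period 7–10 days; open-label phase 12 × 7 = 84 days.

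- 7 / (7 + 84) = 7.7%
- 10 / (10 + 84) = 10.6%
- With the ±3 day EOT window: 7 / (7 + 87) = 7.4% to 10 / (10 + 81) = 11.0%

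Assuming no dropout, 143 patients give 143 × 7/365.25 = 2.7 to 143 × 10/365.25 = 3.9 patient-years inside the table, and 143 × 84/365.25 = 32.9 outside it.

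**3. Where each Protocol 8.4 measure appears.**

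| Measure | By withdrawal arm, withdrawal period | By withdrawal arm, open-label phase | Parts A and B combined, by parent-study arm |
|---|---|---|---|
| Any | SAP 7.2.3 | none | SAP 7.1.3 |
| Serious | none | none | SAP 7.1.3 |
| Severe | none | none | SAP 7.1.3 |
| Drug-related | none | none | SAP 7.1.3 |
| Leading to withdrawal | SAP 5.2.2, by reason, whole of Part B | same table | SAP 7.1.3 |

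So SAP 7.2.3 does not spell out three of the four measures that SAP 2.2.1 itself lists for the withdrawal period.

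**4. Whether the combined tables can recover the contrast.** They cannot.

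- Withdrawal arm was randomised separately, stratified by DRA status (SAP 2.4). The parent-study split does not separate restarted from continued patients.
- The Maintenance Period starts 8 days after the Week 6 visit, so it mixes Part A time with the weeks after restart.
- The incidence tables count each patient once per term, and the EAIR and Kaplan-Meier analyses stop at the first event. A recurrence after restart adds nothing to these if the same term occurred earlier in the period. The event rate does count it, but not by withdrawal arm.
- The EAIR time bands follow weeks of treatment, while patients enter Part B at different study weeks. No band lines up with restart.

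**5. Precision of the missing table.** The documents give no event rates. For an assumed common rate p, the 95% half-width of a risk difference is 1.96 × √(2p(1 − p)/71.5):

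- p = 5%: ±7.1 points
- p = 10%: ±9.8 points
- p = 20%: ±13.1 points

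If none of 71 restarted patients had a given event, the one-sided 95% upper limit is 1 − 0.05^(1/71) = 4.1%.

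**The case against.** The protocol does not ask for this split. Part B is there to test persistence of effect (Protocol 3.2), restart safety is not an objective, and the grouping set for safety data in Protocol 8.3 is overall and by parent-study treatment. The only protocol analysis specified by withdrawal arm is AIMS. The SAP also states that it prevails where it differs from the protocol. All of this stands, so the missing open-label table is not a breach of Protocol 8.4. But SAP 7.2.1 itself chooses withdrawal arm for Part B safety and applies it to EOT for everything except adverse events.

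Open-label events are reported. A reader might infer from SAP 7.2.3 that they are lost; SAP 7.1.3 shows otherwise. What is missing is the comparison by withdrawal arm. Likewise, withdrawals by reason and arm (SAP 5.2.2) largely cover events leading to withdrawal.

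The data are weaker than they look for the first weeks. No visit or call is scheduled between the Post-withdrawal Visit and EOT, so early onset dates would rest largely on recall. The phase is open-label and titration is allowed in it, so doses may diverge between arms. Both points stand and limit what an early window can show. A comparison from restart to EOT depends less on exact dates.

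Precision is modest. That is a reason to keep the tables descriptive, as the SAP's other adverse event tables are.

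**Conclusion.** The concern holds as a gap in analysis scope. SAP 2.2.1 and 7.2.3 reduce five Part B measures to one adverse event table by randomised arm, over about 8%–11% of Part B treatment time. Severe events are dropped, and the open-label phase has only withdrawals by reason by arm. The result rests on planned durations and on 1:1 allocation of the 143 randomised.

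A reader might go further and infer that full-dose restart is unsafe, because Protocol 5.2.5 requires re-titration when a suspension exceeds 7 days. The documents do not support that. Protocol 5.2.3 sets a specific 10-day rule for Part B, and a nominal 7-day gap is within the general rule too. No excess risk is known or assumed here; the point is that the plan would not display one by arm. The primary AIMS endpoint is measured before restart and is unaffected.

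**What to change.** In SAP 2.2.1, restore severe events and extend the Part B adverse event measures beyond the withdrawal period. In SAP 7.2.3, add descriptive summaries by randomised withdrawal arm showing any, serious, severe, drug-related and leading-to-withdrawal events, in two windows defined by onset: the withdrawal period, and restart to EOT. An early window after restart may be added as supportive only, with a note that no contact is scheduled before EOT.

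The cost is a few extra tables from data already collected, with no change to dosing, visits or the primary analysis. At about 71–72 per arm they should carry no tests, and the text should say that they can neither establish nor exclude moderate differences.

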### **7.2.4. Clinical Laboratory Tests**

Summary statistics for serum, chemistry, hematology, and urinalysis laboratory tests will be presented at the Pre-Withdrawal Visit and each Part B visit that this is measured using standard international units. Serum chemistry laboratory tests will also be presented using conventional units. Laboratory tests values and changes from the Pre-Withdrawal Visit to each visit will be

summarized using descriptive statistics. Shifts (below, within, and above the normal range) from the Pre-Withdrawal Visit to each Part B visit will be summarized using patient counts.

#### **7.2.5. Vital Signs**

Summary statistics for resting heart rate and blood pressure, respiration rate, temperature, and weight will be presented at the Pre-Withdrawal Visit and at each Part B visit that these are measured. Summary statistics for orthostatic heart rate and blood pressure will be presented at the Pre-Withdrawal Visit and each Part B visit that this is measured. Vital signs values and changes from the Pre-Withdrawal Visit to each visit the vital sign is measured will be summarized using descriptive statistics.

Orthostatic changes in heart rate and orthostatic changes in blood pressure vital signs values are calculated as the standing minus supine value at the same visit.

#### **7.2.6. Electrocardiogram**

Shifts (normal, abnormal not clinically significant, and abnormal clinically significant) from the Pre-Withdrawal Visit to each Part B visit that this is measured will be summarized using patient counts.

#### **7.2.7. Other Safety Assessments**

Summary statistics for the UPDRS motor score and subscale scores will be presented at the Pre-Withdrawal Visit and each Part B visit that this is measured. UPDRS motor score and subscale scores values and changes from the Pre-Withdrawal Visit to each visit will be summarized using descriptive statistics.

Summary statistics for the BARS summary score will be presented at the Pre-Withdrawal Visit and each Part B visit that this is measured. BARS summary score values and changes from the Pre-Withdrawal Visit to each visit will be summarized using descriptive statistics.

Summary statistics for the HADS depression and anxiety subscales scores will be presented at the Pre-Withdrawal Visit and each Part B visit that this is measured. HADS subscale values and changes from the Pre-Withdrawal Visit to each visit will be summarized using descriptive statistics.

Summary statistics for the C-SSRS last visit version will be presented at the Pre-Withdrawal Visit and each Part B visit that this is measured. Patients with suicidal ideation and behavior items as well as self-injurious behavior without suicidal intent will be summarized at each visit as categorical data using descriptive statistics.

Summary statistics for the ESS total score will be presented at the Pre-Withdrawal Visit and each Part B visit that this is measured. ESS total score values and changes from the Pre-Withdrawal Visit to each visit will be summarized using descriptive statistics.

Summary statistics for the MoCA® total score will be presented at the Pre-Withdrawal Visit and each Part B visit that this is measured. MoCA® total score values and changes from the Pre-Withdrawal Visit to each visit will be summarized using descriptive statistics.

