Protocol Synopsis, Statistics	Safety data will be summarized descriptively for the overall population and based on prior treatment (SD-809 or placebo) in Study SD-809-C-18.	Safety data will be summarized descriptively for the overall population and based on prior treatment (SD-809 or placebo) in the parent study.	Subjects previously participating in another study of SD-809 for the treatment of moderate to severe TD will be allowed to participate in Study SD-809-C-20.
Protocol Synopsis, Statistics	Descriptive statistics of change-from-baseline will utilize the Baseline from Study SD-809-C-18 (C-18 Baseline) and the Baseline from the present study (C-20 Baseline), as appropriate, and will be specified in the Statistical Analysis Plan.	Descriptive statistics of change-from-baseline will use the Baseline from the present study and will be specified in the Statistical Analysis Plan.	Correct inconsistency between synopsis and main text
Protocol Synopsis, Statistics	Descriptive statistics will be used to summarize efficacy measures for the overall population and based on prior treatment (SD-809 or placebo) from Study SD-809-C-18.	Descriptive statistics will be used to summarize efficacy measures for the overall population and based on prior treatment (SD-809 or placebo) in the parent study.	Subjects previously participating in another study of SD-809 for the treatment of moderate to severe TD will be allowed to participate in Study SD-809-C-20.
Schedule of Events (Global change)	Study SD-809-C-18	Parent study	Subjects previously participating in another study of SD-809 for the treatment of moderate to severe TD will be allowed to participate in Study SD-809-C-20.
Schedule of Events	MoCA® at Week 4 and Week 55 visits.	MoCA® deleted at Week 4 and Week 55	Reduce subject burden and decrease potential for practice effects.
Schedule of Events	Return Study Drug at Visit 54	Procedure deleted	Remove duplication of assessment of study drug accountability/compliance

Section	Amendment 01, dated 28 May 2014	Amendment 02, dated 08 July 2014	Reason for Change

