### **2.3. Sample Size and Power Considerations**

Because this is an open-label study, the sample size is not based on statistical considerations.

It is estimated that approximately 91 patients per arm in the Randomized Withdrawal Period will enable a power of at least 90% to detect a beneficial effect of 1.4 points or more in the change from pre-withdrawal to post-withdrawal in centrally read AIMS when the SD-809 arm is compared to placebo, assuming a standard deviation of 2.9 and a 2-sided type I error rate of 5%.

At the time of finalizing this SAP, all patients have started Part B, or completed part A, or have withdrawn from Part A. 143 patients were randomized to Part B, resulting in a power of approximately 80%.

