## **4. GENERAL ISSUES FOR DATA ANALYSIS**

### **4.1. General**

Descriptive statistics for continuous variables include n, mean, standard deviation, standard error, median, minimum, and maximum. Descriptive statistics for categorical variables include patient counts and percentages.

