#### **6.2.2. Efficacy Variables and Analyses**

The primary efficacy variable is the change in total motor AIMS score as assessed by blinded central video rating from Pre-Withdrawal Visit to Post-Withdrawal Visit

Analysis of the change in total motor AIMS score as assessed by blinded central video rating during the Randomized Withdrawal Period (from the Pre-Withdrawal Visit to the Post-Withdrawal Visit) will use an analysis of covariance (ANCOVA) model with the change in total motor AIMS score as the dependent variable. The model will include randomized withdrawal treatment group and DRA status at the Pre-Withdrawal Visit as fixed effects, and the total motor AIMS score at the Pre-Withdrawal Visit value as a covariate. The least squares means of the change in total motor AIMS score will be compared between the SD-809 treatment and placebo groups using a 2-sided test at the  $\alpha=0.05$  level of significance. The SAS code for this test is as follows:

[REDACTED]

The least square (LS) mean and standard error for the treatment groups, and the LS mean difference, 95% confidence interval (CI), and p-value for the comparison (SD-809 vs. placebo) will be presented at the Post-Withdrawal Visit.

Total motor AIMS score values (central reading) and changes from the Pre-Withdrawal Visit to the Post-Withdrawal Visit and EOT visit will be summarized using descriptive statistics for each treatment group. The overall summary will not be presented at the Post-Withdrawal Visit.

In addition, total motor AIMS score (site rating) values and changes from the Pre-Withdrawal Visit to the Post-Withdrawal Visit and EOT visit will be summarized using descriptive statistics for each treatment group. The overall summary will not be presented at the Post-Withdrawal Visit.

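### Part B tabulates UPDRS, BARS, HADS, ESS and MoCA by randomised arm but pre-specifies no between-arm difference or interval, so readers must derive an unadjusted contrast themselves

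*SAP*

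**What the plan says.** SAP 7.2.7 (Part B, Other Safety Assessments) states for the UPDRS: "UPDRS motor score and subscale scores values and changes from the Pre-Withdrawal Visit to each visit will be summarized using descriptive statistics". Parallel sentences cover the BARS summary score, the HADS depression and anxiety subscales, the ESS total and the MoCA total. SAP 7.2.1 fixes the layout: "Summaries will be presented by randomized withdrawal treatment group (SD-809 and placebo) and overall for Part B visits". SAP 4.1 fixes the content: "Descriptive statistics for continuous variables include n, mean, standard deviation, standard error, median, minimum, and maximum". That list contains neither a difference between arms nor a confidence interval.

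SAP 6.2.2 treats centrally read AIMS differently. It fits an ANCOVA with randomised arm, DRA status and the Pre-Withdrawal AIMS score, and reports LS means with standard errors by group, "and the LS mean difference, 95% confidence interval (CI), and p-value for the comparison (SD-809 vs. placebo) will be presented at the Post-Withdrawal Visit". It also withholds the overall (pooled) summary of AIMS at that visit. SAP 7.2.1 makes no such exception for the safety scales.

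Protocol 8.4 lists the scales among the Part B secondary safety endpoints, as observed values and changes. Protocol 8.3 asks for descriptive safety summaries.

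**The concern.** In Part A every patient takes open-label SD-809, and the prior-treatment columns compare two groups that are both on drug. The withdrawal week is the only place in this study where patients are randomised, blind, to stay on SD-809 or stop it. It follows at least 4 weeks on a stable dose and allows no titration. All five scales are recorded before and after it. They cover parkinsonism, akathisia, mood, sleepiness and cognition, which overlap with the adverse events of interest in SAP Appendix A.

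Randomisation protects the difference between the arms, not the change within either one. The plan prints the two changes and stops. A reader can subtract them, but cannot adjust for the Pre-Withdrawal score or the stratification factor from a summary table.

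The overall column adds a smaller problem. At the Post-Withdrawal Visit it averages patients on SD-809 with patients on placebo, and that mean describes neither condition.

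**Working it through.** **The plan's own figure.** SAP 2.3 plans about 91 patients per arm for Part B and claims that this number "will enable a power of at least 90% to detect a beneficial effect of 1.4 points or more in the change". The endpoint is centrally read AIMS, with SD 2.9 and two-sided 5% error.
- n per arm = 2 × (1.960 + 1.282)² × 2.9² / 1.4² = 90.2, rounded up to 91. This matches.
- With the 143 actually randomised, taken as 72 and 71, the noncentral t calculation gives 81.8% power (normal approximation 82.3%). This is consistent with the SAP's figure of about 80%.

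**Precision of the missing contrast, unadjusted.** The documents give no SD for change on any of the five scales, so results are in units of the SD of the change.
- Standard error = √(1/72 + 1/71) = 0.167 SD.
- 95% CI half-width = 1.96 × 0.167 = 0.328, about 0.33 SD. The t multiplier gives 0.331.
- If the SD of the change were 1 to 5 points (an assumed range), the half-width would be 0.33 to 1.65 points.

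**Precision with baseline adjustment.** Assume equal variance σ² before and after, and pre-post correlation r.
- Variance of the change = 2σ²(1 − r).
- Residual variance after ANCOVA = σ²(1 − r²).
- Ratio = (1 − r²) / [2(1 − r)] = (1 + r)/2.

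| r (assumed) | variance ratio | half-width, SD of change |
|---|---|---|
| 0.5 | 0.75 | 0.328 × √0.75 = 0.28 |
| 0.7 | 0.85 | 0.328 × √0.85 = 0.30 |
| 0.8 | 0.90 | 0.328 × √0.90 = 0.31 |

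The interval is 13% narrower at r = 0.5 and 5% narrower at r = 0.8. This counts no gain from DRA status.

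**Estimate or test?** Unadjusted power with 72 and 71 patients is 22%, 43%, 66% and 84% for true differences of 0.2, 0.3, 0.4 and 0.5 SD of the change. An estimate with its interval is useful here. A significance test would mostly invite misreading of null results.

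All figures take 143 as analysed. Patients lacking either score would widen the intervals.

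**The case against.** Four replies have force.

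1. *The contrast is not lost.* A reader might infer that Part B gives only within-arm changes and that the randomised difference can never be known. The documents do not support that. Values and changes appear by randomised arm with n, mean, SD and SE, so an unadjusted difference and interval can be derived. This reply stands, and it limits the point to the absence of a pre-specified, adjusted estimate.

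2. *Bias.* One might also infer that retesting, expectation and regression to the mean distort the Part B results. MoCA is repeated after 7 to 10 days, and Amendment 02 removed two other MoCA visits partly to "decrease potential for practice effects", the other reason being subject burden. But these effects act alike on both blinded arms in expectation and cancel in the comparison. They mislead only a reader who looks at one arm alone. What remains is a chance imbalance at the Pre-Withdrawal Visit, which the raw change difference does not handle well and ANCOVA does.

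3. *The protocol asked for this.* Protocol 8.3 and 8.4 call for descriptive safety reporting, and Protocol 3.2 gives Part B's purpose as persistence of effect. This stands: there is no conflict between the two documents.

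4. *Limited meaning.* The first objective concerns long-term maintenance therapy. The contrast shows 7 to 10 day reversal in patients already stable on a dose they tolerate, and cannot attribute long-term effects to the drug. All patients also came from placebo-controlled parent studies, so other randomised data may exist; how they were analysed is not shown here. This stands and belongs in the text beside the estimates.

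**Conclusion.** The point holds as a modest omission. For UPDRS, BARS, HADS, ESS and MoCA the SAP pre-specifies no between-arm difference or interval, although it does so for centrally read AIMS from the same visits and the same randomisation. The main gain from correcting this is a randomised estimate defined in advance that uses the stratification factor and each patient's own Pre-Withdrawal score. The gain in precision is secondary: a half-width of about 0.33 SD of the change becomes about 0.28 to 0.31 SD. That range rests on a 72/71 split with all 143 analysed, equal pre and post variances, and r of 0.5 to 0.8. The variances and correlation are assumptions, and a higher r would shrink the gain further.

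The documents do not support reading this as a departure from the protocol, as a biased safety analysis, or as lost evidence on long-term safety.

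**What to change.** In SAP 7.2.7, at the Post-Withdrawal Visit only (by EOT both arms are back on open-label SD-809):
- Report the LS mean difference, SD-809 minus placebo, with 95% CI for the UPDRS motor score, BARS summary score, HADS depression, HADS anxiety, ESS total and MoCA total.
- Use the 6.2.2 ANCOVA with arm, DRA status and that scale's own Pre-Withdrawal score, in patients with both scores, and state the number analysed.
- Label the intervals descriptive, with no p-values.
- Drop the pooled overall column at that visit, as 6.2.2 already does for AIMS.
- State that the contrast reflects 7 to 10 day reversal in stable patients who tolerate the drug, and that normal-theory intervals are approximate for bounded scores such as the BARS summary (0 to 9).

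The change should be made before the Part B treatment codes are released; after that, the estimates should be labelled post hoc.

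The cost is a few lines of SAP text and reuse of an existing model. No new data, visits or patients are needed, and the scoring and missing-item rules are already in SAP 4.3 and 4.4. The downside is six intervals without multiplicity control, which the descriptive label addresses.
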